3.2 WILL EXISTING RECORDS BE USED TO IDENTIFY AND CONTACT / RECRUIT SUBJECTS?

Examples of existing records - directories, class roster, university records, educational records

No, go to question 3.3

Yes, answer questions within table

IF YES

Are these records private or public?

Public

Private, describe the researcher's privilege to the records: **Participants will be contacted if they have given prior permission (through a previous informed consent form) or by completion of a confidential pre-screening questionnaire.**

Will student, faculty, and/or staff records or contact information be requested from the University?

No

Yes, visit the following link for further information: <http://www.policies.vt.edu/index.php> (policy no. 2010)

3.3 DESCRIBE RECRUITMENT METHODS, INCLUDING HOW THE STUDY WILL BE ADVERTISED OR INTRODUCED TO SUBJECTS:

Participants will be recruited from the community via advertisements such as posted flyers, internet (e.g., Facebook or other websites), etc. To the extent possible, we will attempt to minimize obstacles to participation. For example, travel barriers may be addressed by providing transportation or parking costs for participants, and scheduling barriers will be minimized by offering a flexible study visit schedule. Compensation may be provided for travel costs and time. All methods and measures will be conducted using standard operating procedures, and all staff (including recruitment staff) will be provided with online human subjects training. We have a history of successful recruitment of cigarette smokers into research programs. All participants will enroll on a voluntary basis.

3.4 PROVIDE AN EXPLANATION FOR CHOOSING THIS POPULATION:

Note: the IRB must ensure that the risks and benefits of participating in a study are distributed equitably among the general population and that a specific population is not targeted because of ease of recruitment.

Cigarette smokers will be recruited for this study. This population was chosen because the current experiment entails smoking cigarettes. Non-smokers would not be appropriate because nicotine and tobacco smoke may make individuals that do not regularly smoke feel ill. Otherwise healthy individuals are sought to minimize any ill effects that exposure to nicotine and cigarette smoke may cause.

Section 4: Consent Process

For more information about consent process and consent forms visit the following link: <http://www.irb.vt.edu/pages/consent.htm>

If feasible, researchers are advised and may be required to obtain signed consent from each participant unless obtaining signatures leads to an increase of risk (e.g., the only record linking the subject and the research would be the consent document and the principal risk would be potential harm resulting in a breach of confidentiality). Signed consent is typically not required for low risk questionnaires (consent is implied) unless audio/video recording or an in-person interview is involved. If researchers will not be obtaining signed consent, participants must, in most cases, be supplied with consent information in a different format (e.g., in recruitment document, at the beginning of survey instrument, read to participant over the phone, information sheet physically or verbally provided to participant).

4.1 CHECK ALL OF THE FOLLOWING THAT APPLY TO THIS STUDY'S CONSENT PROCESS:

- Verbal consent will be obtained from participants
- Written/signed consent will be obtained from participants
- Consent will be implied from the return of completed questionnaire. Note: The IRB recommends providing consent information in a recruitment document or at the beginning of the questionnaire (if the study only involves implied consent, skip to Section 5 below)
- Other, describe:

4.2 PROVIDE A GENERAL DESCRIPTION OF THE PROCESS THE RESEARCH TEAM WILL USE TO OBTAIN AND MAINTAIN INFORMED CONSENT:

Potential participants will be provided with the written consent form prior to visiting FBRI at VTC (e.g., by email), if they wish. They will also be given additional time in a quiet room at FBRI at VTC to read the form. FBRI at VTC research staff will review each element of the written consent form with the potential participant. The potential participant will be given the opportunity to ask questions and will have as much time as they need to decide whether they would like to participate in the study. They will be encouraged to speak with whomever they wish before making this decision. Staff will reiterate that the potential participant can choose to decline participation in the study at that time or at any time thereafter without consequence. The potential participant and person obtaining consent will sign the consent form after the potential participant verbally states that s/he understands the conditions of the study, has no more questions, and chooses to participate.

4.3 WHO, FROM THE RESEARCH TEAM, WILL BE OVERSEEING THE PROCESS AND OBTAINING CONSENT FROM SUBJECTS?

Study team members that have been delegated this responsibility by the PI.

4.4 WHERE WILL THE CONSENT PROCESS TAKE PLACE?

In a quiet room at the FBRI at VTC.

4.5 DURING WHAT POINT IN THE STUDY PROCESS WILL CONSENTING OCCUR?

Note: unless waived by the IRB, participants must be consented before completing any study procedure, including screening questionnaires.

Consenting will occur prior to any study procedures.

4.6 IF APPLICABLE, DESCRIBE HOW THE RESEARCHERS WILL GIVE SUBJECTS AMPLE TIME TO REVIEW THE CONSENT DOCUMENT BEFORE SIGNING:

Note: typically applicable for complex studies, studies involving more than one session, or studies involving more of a risk to subjects.

Prior to visiting the lab, participants will be given the option to receive a copy of the consent form before attending a consent session. They will be able to receive the consent copy via e-mail, mail, or in person if they wish. The potential participant will be given the opportunity to ask questions and will have as much time as they need to decide whether they would like to participate in the study. They will be encouraged to speak with whomever they wish before making this decision.

Not applicable

Section 5: Procedures

5.1 PROVIDE A STEP-BY-STEP THOROUGH EXPLANATION OF ALL STUDY PROCEDURES EXPECTED FROM STUDY PARTICIPANTS, INCLUDING TIME COMMITMENT & LOCATION:

We will first ask potential participants a series of brief screening questions to determine whether they will likely meet eligibility criteria. Individuals who are eligible based on the screening questionnaire will be scheduled for an informed consent session.

The current study will take place over approximately 10 laboratory sessions at the FBRI at VTC's Addiction Recovery Research Center including the consent session (approximately 1 hour). Following informed consent, participants may also be asked to leave a baseline CO sample and urine sample (females only). The urine sample will be tested for pregnancy in females. Weight will also be measured. We have included three screening questions that ask about intentions to quit and desire to seek treatment. If a participant reports discordant answers on the intentions to quit or seek treatment questions (e.g., indicates no plans to quit but expresses an interest in treatment), we will ask a clarifying question that more directly assesses our stated exclusionary criteria of an immediate plan to quit smoking. For these participants, a question will appear that asks: "You expressed some interest in either quitting smoking or smoking cessation treatment. Do you

have plans for a quit attempt in the next 30 days?" If the participant answers that s/he plans to quit, s/he will be excluded from participating in the 7 cigarette purchase sessions and provided the [name] ([name]) hotline, which can connect callers to a variety of local resources for quitting. However, the participant will be allowed to complete the 7 cigarette purchase sessions if there are no plans to quit in the next 30 days. All participants will complete the assessment session (described below) and only participants who meet all eligibility criteria will go on to complete the 7 cigarette purchase sessions, each at least two days apart. There will be at most two cigarette purchase sessions per week.

Although we only anticipate that a participant's total commitment will not be longer than 5 weeks (2 purchase sessions/week [4 weeks] + 1 assessment session [1 week or less]), if more than 7 sessions are required (due to factors outside of the control of participants, for example, a participant is eligible to start a purchase session but blood is unable to successfully be drawn), at the beginning of the first session of the 6th week (6 weeks from the initial assessment session) we will obtain a urine sample (for females only) to verify the participant is not pregnant. This is to minimize the risk of the investigational tobacco product under study. If the female participant tests positive for pregnancy, she will be withdrawn from the study. Following withdrawal, we will follow-up with the participant (via phone call) until the outcome of the pregnancy is established.

One Assessment session (approximately 1 hour). The first lab session will be the assessment session to collect information from participants on substance use patterns and severity, as well as the results of behavioral and cognitive tasks that we think may inform or compliment the results from the main study (see appendix for examples). This may be on the same day as the consent session and all participants who provide informed consent will complete this session. Participants who are not eligible to continue (e.g., report immediate plans to quit) will not continue to complete the following 7 cigarette purchase sessions.

Seven Cigarette purchase sessions (approximately 1.5 hours). In the remaining seven cigarette purchase sessions (may be more than 7 due to factors outside of the control of participants, for example, a participant is eligible to start a purchase session but blood is unable to successfully be drawn), we will assess the behavioral economic demand intensity and elasticity of cigarettes with different nicotine concentrations. During each of these 7 cigarette purchase sessions, participants will consume either their usual brand of cigarette, an experimental cigarette containing 0.4 mg/g, 1.4 mg/g, 2.5 mg/g, 5.6 mg/g, or 17.4 mg/g nicotine, or a nonusual brand, commercially available cigarette. All but the nonusual brand, commercially available cigarettes will be presented in a randomized order across participants to control for any order effects; the nonusual brand, commercially available cigarette will be administered during the 7th session. The participants' preferred brand of conventional cigarettes will be used for the appropriate session. The cigarette doses will be blinded so the participants are not aware of the dose they will administer, leaving only subjective effects. Participants will be asked to abstain from consuming nicotine for 12 hours prior to each cigarette purchase session. Abstinence will be verified with breath CO at the beginning of the session, which will need to be <8 ppm to participate. If participants do not meet this criterion, they will be allowed to reschedule the session and try again. After repeated failed attempts, participant participation may be terminated. Each purchase session will begin with baseline ratings of nicotine craving, current drug effect, breath CO, and nicotine withdrawal symptoms. The baseline blood draw will also be collected at this time. Blood will be drawn with a catheter throughout the session by a registered nurse or other personnel with phlebotomist training to measure plasma nicotine levels during the sessions. The catheter will be removed at the end of each purchase session. Snacks and/or beverages will be available for the participants to consume, at their own discretion, should they begin to feel light-headed.

Five minutes into the session, participants will consume the cigarette randomly chosen for that session. Consumption will be modeled after the initial consumption period of Vansickel and Eissenberg (2013) and will consist of 10 puffs with each puff initiated 30 seconds after the previous. Consumption will occur in ventilated booths located in the Addiction Recovery Research Center specifically designed for this purpose.

To measure how the subjective effects and plasma nicotine levels dissipate over the course of an hour, visual analogue scales (VAS) ratings, breath CO, and 7 blood draws (3 mL each), including the baseline one, will be collected throughout the session (baseline and at minutes 10, 15, 20, 30, 45, and 60). The catheter will be flushed with saline (1 mL) after each draw, followed by a 1 mL discard draw to remove the saline flush. No heparin will be used. The 3 mL blood drawn per draw would result in 21 mL total blood per session and 126 mL total over the six cigarette purchase sessions. To maintain sterility, the site is covered with a Tegaderm, the port is cleansed with alcohol, and the staff handle the IV site with clean, gloved hands. After the VAS ratings at one of the timepoints, participants will complete hypothetical purchase tasks for the product they just consumed and some brief discounting tasks, similar to the ones completed during the

assessment session. The value of the nicotine product just consumed will be assessed by asking how many cigarette puffs the participant would purchase if they were available at different prices. Hypothetical purchase tasks are typically used to measure the consumption of a product already familiar to the participant. In this project, we will use this procedure in a novel way by asking participants to indicate their consumption decisions for a product they just consumed, but remain blinded to the nicotine content. This will prevent their responses being biased by preconceptions of dose information, instead tying purchasing behavior to the experienced effects of each dose.

Blood samples will be de-identified (i.e., only labeled with an arbitrary ID) and brought to or sent for testing to a laboratory that offers such services (e.g., LabCorp or Solstas at Carilion). Blood samples will only be tested for nicotine and the primary metabolite of nicotine (cotinine), after which they will be destroyed. In the event a researcher or other staff person is improperly exposed to a participant's blood, it will be tested for the presence of HIV, the Hepatitis B Virus, and the Hepatitis C Virus. The research team will follow proper procedures for testing and reporting as outlined by Virginia State Law, which includes sending the sample to a certified laboratory. Should a participant's blood require testing, s/he will be informed of the test results and provided with the opportunity to receive appropriate and timely counseling. In addition, the results will be sent to the local health department.

One Cigarette Comparison session (approx. 1.5 hours). After completing all blood draw sessions, participants may come back for one final in-lab session. No blood will be taken during this session. Participants will be provided an array of cigarettes consumed during the previous blood draw sessions. Cigarettes will be labeled with an arbitrary code (e.g., A, B, C) and participants may be told which of the blood draw sessions they consumed each cigarette. In the ventilated smoking booth, participants will take one to two puffs of each cigarette. Immediately after puffing the cigarette, participants will complete the tasks similar to those completed during the blood draw sessions (e.g., VAS ratings, hypothetical purchase tasks). Participants will take the one to two puffs approximately every 10 minutes and will be provided water or another bland beverage to cleanse the palate between puffs. After experiencing all cigarettes, participants will rank order the cigarettes (1-X [X being the number of cigarettes in the array] with 1 being the most preferred). Participants will also answer questions that directly compare each of the cigarettes (e.g., Assuming all of the cigarettes you just tried were available for you to purchase, would you pay to purchase and consume or would you pay to avoid and not consume this specific cigarette? And depending on their answer, What is the most you would pay to smoke 1 of these cigarettes OR What is the most you pay to avoid smoking 1 of these cigarettes).

5.2 DESCRIBE HOW DATA WILL BE COLLECTED AND RECORDED:

All data will be collected and recorded with custom-built computer programs and/or standardized paper forms by trained study staff.

5.3 DOES THE PROJECT INVOLVE ONLINE RESEARCH ACTIVITIES (INCLUDES ENROLLMENT, RECRUITMENT, SURVEYS)?

View the "Policy for Online Research Data Collection Activities Involving Human Subjects" at
<http://www.irb.vt.edu/documents/onlinepolicy.pdf>

No, go to question 6.1

Yes, answer questions within table

IF YES

Identify the service / program that will be used:

- www.survey.vt.edu, go to question 6.1
- Blackboard, go to question 6.1
- Center for Survey Research, go to question 6.1
- Other

IF OTHER:

Name of service / program: REDCap, Craigslist, Facebook, Qualtrics

URL: <http://www.redcap.com/>, <https://www.craigslist.org/>, <https://www.facebook.com/>, <https://virginiatech.qualtrics.com>

This service is...

- Included on the list found at: <http://www.irb.vt.edu/pages/validated.htm>
- Approved by VT IT Security
- An external service with proper SSL or similar encryption (https://) on the login (if applicable) and all other data collection pages.
- None of the above (note: only permissible if this is a collaborative project in which VT individuals are only responsible for data analysis, consulting, or recruitment)

Section 6: Risks and Benefits

6.1 WHAT ARE THE POTENTIAL RISKS (E.G., EMOTIONAL, PHYSICAL, SOCIAL, LEGAL, ECONOMIC, OR DIGNITY) TO STUDY PARTICIPANTS?

One risk of participation is embarrassment that may come from answering sensitive questions related to medical, psychiatric, and/or drug use history. Loss of confidentiality is another risk of participation. Participants may also experience discomfort during the blood draw sessions.

6.2 EXPLAIN THE STUDY'S EFFORTS TO REDUCE POTENTIAL RISKS TO SUBJECTS:

Participants will be screened, using medical history and structured interviews, for a history of medical contraindications (e.g., pregnancy), and current unstable medical illnesses. The study will occur in our facilities at the FBRI at VTC. Participants will be free to withdraw from the study at any time, and their refusal to continue will not affect other medical care associated with Carilion. Participants who become pregnant during the course of the study will be withdrawn. Following withdrawal, these participants will be followed up (via phone) to determine the outcome of the pregnancy (e.g., were there any complications?). In addition, if participants develop medical problems or experience adverse events during the course of the study, assessments to determine whether participants should continue in the study and/or continue to use study products will be conducted and necessary referrals will be provided. Using only ID numbers and keeping all data in secure locations and/or in locked offices accessible only to trained study team members will protect confidentiality. Computer databases will have coded identifiers. These screening, monitoring, and confidentiality procedures have been in effect for more than 10 years and for more than 2,000 subjects across the various protocols employed by our group across various institutions.

6.3 WHAT ARE THE DIRECT OR INDIRECT ANTICIPATED BENEFITS TO STUDY PARTICIPANTS AND/OR SOCIETY?

Participants might benefit from education about research participation. The project involves minimal risk to confidentiality or other personal rights or to physical or emotional health. Thus, the expected benefits outweigh the very minimal risks to participants.

Section 7: Full Board Assessment

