9.1 WILL SUBJECTS BE COMPENSATED FOR THEIR PARTICIPATION?

No, go to question 10.1

Yes, answer questions within table

IF YES

What is the amount of compensation? Compensation for participation will be as follows:

\$20.00 for completion of informed consent

\$40.00 for the assessment session

\$40.00 for each of the completed cigarette purchase session (7 total)

\$20.00 for the cigarette comparison session

\$75.00 bonus for completing all sessions

\$10 for cigarette purchase sessions that are discontinued due to situations outside of the control of participants (i.e. a participant is eligible to begin a cigarette purchase session, but the session is discontinued due to an inability to successfully draw blood)

Combined, the subjects could be compensated approximately \$435 by completing all aspects of the experiment.

To allow for payments that are both convenient and rapidly available, we may pay participants with reloadable prepaid cards through Greenphire ClinCard (www.greenphire.com), an FDIC-insured payment provider that specializes in clinical trial stipend payments that comply with IRB privacy regulations and considerations. At the beginning of the study, the participant will receive a prepaid MasterCard debit card that can be used anywhere that accepts MasterCard. As payments are earned in the course of the study, additional funds will be added to the account for that participant. Funds are immediately available when added and participants can check their balance as desired. This system will allow frequent, immediately available payments. Payments may also be made via check, however remote debit card payments will be used most often.

Will compensation be prorated?

Yes, please describe: **Subjects will be compensated based on what study procedures he/she has completed.**

No, explain why and clarify whether subjects will receive full compensation if they withdraw from the study?

Unless justified by the researcher, compensation should be prorated based on duration of study participation. Payment must not be contingent upon completion of study procedures. In other words, even if the subject decides to withdraw from the study, he/she should be compensated, at least partially, based on what study procedures he/she has completed.

Section 10: Audio / Video Recording

For more information about audio/video recording participants, visit the following link: <http://www.irb.vt.edu/pages/recordings.htm>

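### Experiment 1's repeat pregnancy test is triggered by session count, not elapsed time, so an overrun that adds no session leaves investigational cigarettes to be smoked without a retest (minor)

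*Combined protocol and SAP*

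**What the plan says.** All of this is in section 5.1 of the Experiment 1 application (IRB v.8) unless noted.

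- **Baseline test.** After consent, "participants may also be asked to leave a baseline CO sample and urine sample (females only"); the women's sample is tested for pregnancy.
- **Repeat test: whether.** The plan expects a commitment of no more than five weeks. It then orders a second urine test "if more than 7 sessions are required (due to factors outside of the control of participants"), with an unsuccessful blood draw as the example.
- **Repeat test: when.** "at the beginning of the first session of the 6th week (6 weeks from the initial assessment session) we will obtain a urine sample". The stated reason is to limit risk from the investigational product. A woman who tests positive is withdrawn.
- **Pace.** "There will be at most two cigarette purchase sessions per week", at least two days apart. No minimum pace is set, and section 3.3 promises flexible scheduling.
- **Failed abstinence check.** "If participants do not meet this criterion, they will be allowed to reschedule the session and try again". The next sentence lets the team end participation after repeated failures, without fixing a number.
- **Which sessions are investigational.** Sessions 1-6 are the usual brand and five investigational cigarettes in random order; "the nonusual brand, commercially available cigarette will be administered during the 7th session".
- **Comparison session.** "After completing all blood draw sessions, participants may come back for one final in-lab session", taking one or two puffs of each cigarette in the array. It has no deadline and no test, and the five-week sum leaves it out.

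No other visible part of the Experiment 1 documents requires a retest. Section 6.2 withdraws women who become pregnant but supplies no test.

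**The concern.** The retest exists to catch a pregnancy that began after baseline, before the woman smokes more of an investigational product. That risk grows with time since the last test. The rule measures something else, namely how many sessions are needed and why. Two women with the same delay and the same cigarettes left can therefore be treated differently: the one whose blood could not be drawn is tested, and the one who came once a week is not.

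The plan gives its own reasons to care. Section 3.4 of Experiment 2, which uses the same five nicotine concentrations, says the fetal risk of these products is not known. Section 5.1 of Experiment 2 allows a retest before its added sessions, which use investigational cigarettes. Experiment 1's comparison session has no counterpart.

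What is at stake is participant safety and whether staff can apply the rule. No endpoint, sample size or error rate depends on it.

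**Working it through.** **Inputs (Experiment 1, section 5.1).** Seven purchase sessions; at most two a week; five weeks planned, counting up to one week for assessment; five of the six randomised cigarettes investigational; 10 puffs per purchase session; one or two puffs per cigarette at the comparison session.

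**1. The plan's own figure.** Weeks = ceil(7/2) + 1 = 4 + 1 = 5. This reproduces the stated five weeks, with the assessment week inside it.

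**2. The two test dates.** Take assessment as day 0 and week = floor(day/7) + 1. Five weeks are days 0-34, so the 6th week starts on day 5 × 7 = 35. Six weeks from assessment is day 6 × 7 = 42, the first day of week 7. The two differ by 7 days. A visit on days 35-41 is due for a test on one reading and not on the other.

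**3. Session count does not track time.** At two a week from the week after assessment, an 8th session falls in week 1 + ceil(8/2) = 5. More than seven sessions can thus fit within five weeks. Step 4 shows the reverse, seven sessions running past week 5.

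**4. Slow pace, exactly seven sessions.** At one a week from day 7, the sessions fall on days 7, 14, 21, 28, 35, 42 and 49.
- On the day-35 reading, randomised sessions 5 and 6 are late. At least one is investigational, because only one of the six is the usual brand.
- On the day-42 reading, only session 6 is late. It is investigational with probability 5/6.
- If purchase sessions start in the assessment week, only session 6 is late on the day-35 reading. None is late on the day-42 reading unless one more week is lost.

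The total stays at seven throughout, so no test is triggered. One a week is a scenario; the plan expects two.

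**5. Rescheduled CO failures, two slots a week.** Assumption: each failed check uses up one weekly slot, and the rescheduled visit is not an extra session. Session 6 in slot s falls in week offset + ceil(s/2). The offset is 1 if purchase sessions start the week after assessment and 0 if they start in the same week. Lost slots before session 6 is late:

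| Start of purchase sessions | Day-35 reading (week ≥ 6) | Day-42 reading (week ≥ 7) |
|---|---|---|
| Week after assessment | 3 (slot 9) | 5 (slot 11) |
| Assessment week | 5 (slot 11) | 7 (slot 13) |

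Three failed blood draws would bring the total to 7 + 3 = 10 sessions and meet the condition. Three failed CO checks leave it at 7. If the retry fits in the same week, this route adds no delay.

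**6. Comparison session, no earlier delay.** At two a week, session 7 falls in week 1 + ceil(7/2) = 5, or week 4 if sessions start in the assessment week. The comparison visit is late if held 1 (or 2) weeks after that week on the day-35 reading, and 2 (or 3) weeks after on the day-42 reading. It involves up to 5 × 1 to 5 × 2 = 5-10 investigational puffs.

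**7. What is not exposed.** Session 7 is a commercial cigarette. The gap concerns randomised sessions 1-6 and the comparison session only.

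**The case against.** The strongest reply is about intent. The paragraph opens with the five-week expectation and ends with a test in week 6, so its natural sense may be that any woman still enrolled after five weeks is tested, with extra sessions named as the foreseen way of getting there. That is plausible. But the sentence makes the test conditional on the session count, and the application's closing statement requires the protocol to be followed. If intent was wider, the amendment simply records it.

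A reader might go further and infer that only failed blood draws count as outside the participant's control, because section 9.1 pays for sessions stopped "due to situations outside of the control of participants (i.e. a participant is eligible to begin a cigarette purchase session" but blood could not be drawn. The documents do not support that. Section 9.1 is a payment rule, and section 5.1 gives the blood draw only as an example. The point does not need the narrow reading, because slow pace and a late comparison visit add no purchase session whatever the cause.

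Three replies stand in part.

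- **CO route.** Its delay is assumed. If a failed attempt is not a session, the weekly cap does not count it and a same-week retry is possible. If it is a session, the count may be met and only the cause clause is left to decide. The discretion to end participation after repeated failures also limits this route.
- **Departures from plan.** One session a week is slower than planned, and the comparison session is optional.
- **Test date.** The bracket can be read as defining the 6th week. But the same sentence counts the assessment week within the five, so the two dates still differ. This is secondary.

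**Conclusion.** The concern holds in this form: the only repeat pregnancy test in Experiment 1 depends on session count and cause, so an overrun that adds no session triggers no test, even with investigational cigarettes left to smoke after week 5. For slow pace and the comparison session this follows from the count alone. For CO failures it also rests on the two assumptions in step 5 of the working. The 7-day difference between the two test dates is real but secondary.

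Severity is minor. The number of women affected cannot be computed from the documents and is likely small. Exposure is at most 10 puffs per session, in women who already smoke at least five cigarettes a day (section 3.1). Section 3.1 excludes women planning pregnancy or unwilling to use contraception, and section 6.2 withdraws those who become pregnant. These safeguards lower the risk but do not detect an unrecognised pregnancy, which is the retest's job.

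Two stronger inferences are not supported. One is that the gap affects the trial's results: nothing in the demand or pharmacokinetic analyses depends on it. The other is that women may enter untested, because the baseline sample is worded as something they may be asked for: pregnancy is exclusionary and section 5.1 says the sample will be tested, so I take the baseline test as done. The statement that no other retest is required applies to the visible text only, since consent pages were removed.

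**What to change.** In section 5.1 of Experiment 1, delete the session-count and cause condition and use one date. Any woman with an investigational cigarette still to smoke, in randomised sessions 1-6 or at the comparison session, gives the existing urine test before smoking at her first visit on or after that date. Day 35 from assessment fits the five-week plan; the investigator and IRB may prefer day 42. A woman with only the commercial session 7 left needs no test.

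The cost is one amended sentence and one extra urine test, of the kind already used at baseline, per woman who overruns with an investigational cigarette still to smoke.
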